3.1 Study design

This is a study of multiple doses of inhaled QBW276 in patients with CF on top of Standard of Care, including hypertonic saline, CFTR potentiators and correctors, if applicable. The study will be divided into three cohorts. Cohorts 1 and 2 are designed to be a randomized, double-blind, placebo-controlled, parallel arm multiple ascending dose study of the safety, tolerability, PK and preliminary efficacy of inhaled QBW276 over 1 week (cohort 1) and 2 weeks (cohort 2) in patients with CF regardless of their genotype. The primary rationale for cohorts 1 and 2 will be to assess PK, safety and tolerability in CF. Cohort 3 is a randomized, double-blind, placebo-controlled, cross-over design multiple dose study of the efficacy, safety, tolerability, and PK of inhaled QBW276 over 4 weeks in patients with CF who are homozygous for the F508del mutation. The primary rationale for cohort 3 will be to assess efficacy in a high unmet need CF patient population.

Figure 3-1 Schematic for study design

Cohort 1 will receive 3 mg bid dose (6 mg/day) or placebo over 1 week. This dose selection is based on safety and tolerability data obtained from healthy volunteers in the first-in-human CQBW276X2101 study. Upward, downward, or repeat dosing will continue in cohorts 2 and 3,

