as long as the systemic exposure cap based on pre-clinical data or a clinical maximum tolerated dose (MTD) is not exceeded. Cohorts 1 and 2 will enroll 8 patients each, with 6 patients randomized to receive active drug and 2 patients randomized to receive matching placebo. Cohort 1 will be dosed for 1 week while cohort 2 will be dosed for 2 weeks. Cohort 2 will be initiated only after cohort 1 has completed dosing. Cohort 2 may be skipped if safety, tolerability, PK and PD data from cohort 1 are found favorable to proceed directly to cohort 3. In cohorts 1 and 2, patients may be replaced if they do not complete the study duration for reasons other than safety to obtain 8 completers in each cohort. If a patient has participated in cohort 1, he/she may qualify to participate in cohort 2 contingent upon approval from the sponsor, as long as he/she has been through a 4 week wash-out between dosing in the two cohorts, and has not experienced any significant AEs since enrollment in cohort 1. This will ensure that no patient receives more than 4 weeks of the investigational drug QBW276 in his/her lifetime until further supportive toxicology studies are conducted in the drug's development program.

NOTE: No patient randomized to cohort 1 or 2 will be eligible for cohort 3.

Cohort 1 and 2

Cohorts 1 and 2 will consist of a 21 day screening period followed by a baseline visit and a 7 or 14 day Treatment Period in cohort 1 and 2, respectively. Adequate windows will be provided for patient's convenience. QBW276 will be administered on top of the patient's usual standard of care medications.

Study inclusion/exclusion criteria as well as medication use will be assessed at screening. Patients who meet the inclusion/exclusion criteria at screening will report to the study site on Day -1 at a time specified by the investigator, for the baseline assessments. All baseline safety evaluation results must be available prior to dosing on Day 1, hence, Day -1 assessments can be carried out up to 72 hours prior to Day 1 dosing.

Patients who meet all of the inclusion and none of the exclusion criteria at baseline will then report to the study site on Day 1 and will remain in the clinic until at least 6 hours after the first dose in the morning.

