For Cohort 3, patients will be randomized to one of two treatment sequences: QBW276 in Period 1 and Placebo in Period 2 or Placebo in Period 1 and QBW276 in Period 2. Based on drop-out rates observed during conduct of the study, up to 40 patients will be randomized to ensure that at least 24 patients complete the study. After a 45 day screening period, patients who meet all inclusion and exclusion criteria will receive drug for 4 weeks and placebo for 4 weeks, separated by a washout period of approximately 3 to 4 weeks in patients who cycle inhaled antibiotics. Washout period may be shortened to 2 weeks in patients who do not cycle inhaled antibiotics. QBW276 will be administered on top of the patient's usual standard of care medications. For patients on cyclic inhaled antibiotics, baseline for periods 1 and 2 will commence on approximately day 7 (0/+3) of the patient's standard of care cyclic inhaled antibiotic regimen. Patients who use the same inhaled antibiotic throughout the year may start the study on any antibiotic day.

Screening and baseline visits for cohort 3 will be similar to the respective visits in cohorts 1 and 2. On Day 1 of cohort 3, pre-dose safety, efficacy Corporate Confidential Information will be performed. Following the pre-dose procedures eligible patients will be dosed for up to 28 days. Post-dose evaluations will include routine safety evaluations and blood for PK assessments. The patients will be asked to return to the study site for follow-up visits on Days 7, 14, 21, and 28 after which they will undergo an approximately 3 to 4 week wash-out period (may be shortened to 2 weeks in patients who do not cycle inhaled antibiotics) prior to cross-over to the opposite arm, and follow a similar visit schedule until End of Study assessment approximately 7 days after the last visit in the second period. All patients will undergo the same assessments regardless of their dose.

Efficacy will be evaluated by spirometry and responses to the respiratory domain of the CFQ-R. Safety will be monitored by assessment of vital signs, physical examination, ECG, clinical laboratory evaluations (hematology, blood chemistry, and urinalysis), urine electrolytes, aldosterone in plasma, and monitoring of adverse events (AEs) throughout the study.

Corporate Confidential Information

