3.3 Rationale of dose/regimen, duration of treatment

Cohorts 1 and 2: Up to 16 patients with CF (8 patients in each cohort, regardless of genotype) will complete 7 to 14 days of inhaled QBW276 or placebo via the concept 1 inhaler. Cohort 1 will receive 3 mg bid dose, which is based on safety, tolerability, PK and adverse event data obtained from the CQBW276X2101 healthy volunteer study.

Cohort 3: Cohort 3 will be restricted to CF patients who are homozygous for the F508del mutation, Corporate Confidential Information

This may also help reduce variability in baseline characteristics of patients in this small study. Patients will receive 4 weeks of drug and 4 weeks of placebo, separated by a washout period of approximately 3 to 4 weeks in patients who cycle inhaled antibiotics. Washout period may be shortened to 2 weeks in patients who do not cycle inhaled antibiotics. For patients on cyclic inhaled antibiotics, the baseline visit will be on approximately the 7th day (0/+3 days) of inhaled antibiotic use during their 28 day antibiotic cycle. Patients who use the same inhaled antibiotic throughout the year may start the study on any antibiotic day. Patients will take their inhaled antibiotic therapy at approximately the same time during the study as they would usually at home Corporate Confidential Information

Cohort 1 - The first cohort will be dosed at 3 mg bid to begin assessment of safety and tolerability in CF because this dose has been
and found to be safe and well tolerated. Corporate Confidential Information
Corporate Confidential Information

The dose and frequency will be proposed by the sponsor at the data review, and will require approval from the designated site Investigator(s) and endorsement from the independent DMC. The maximum dose in cohort 3 will be expected to not exceed 6 mg bid. Corporate Confidential Information

PK data will be assessed after each dose cohort completes the study to confirm that an appropriate exposure margin exists before escalating to the next dose level.

Corporate Confidential Information

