6.2 Treatment arms

Cohort 1 and 2:

Patients will be assigned to one of the following 2 treatment arms in a ratio of 3:1. In each cohort (n=8), there will be 6 patients randomized to receive QBW276 and 2 patients randomized to receive Placebo.

Study treatments are defined as:

Cohort 1:

- QBW276 3mg bid
- Placebo to QBW276 3mg bid

Cohort 2:

- QBW276 Dose 6 mg bid
- Placebo to QBW276 Dose 6 mg bid

Cohort 3:

Corporate Confidential Information

Patients will be randomly assigned to one of the following 2 treatment sequences.

Study treatments are defined as:

- A: QBW276 Dose B (no more than 6 mg bid)
- B: Placebo to QBW276 Dose B (no more than 6 mg bid)

Corporate Confidential Information

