EPOCH	SCREENING		TREATMENT PERIOD 1								TREATMENT PERIOD 2					
	Screening	Baseline	Day 1	Day 7	Day 14	Day 21	Day 28	Washout	Baseline/ET/EOS ²	Day 57	Day 63	Day 70	Day 77	Day 84	ET/EOS	
Visit Name	Screening	Baseline	Day 1	Day 7	Day 14	Day 21	Day 28	Washout	Baseline/ET/EOS ²	Day 57	Day 63	Day 70	Day 77	Day 84	ET/EOS	
Visit Numbers ¹	1	2	101	103	104	105	106	TC	199	201	202	203	204	205	299	
Study Day(s)	-45 to -14	-7 to -4	1	7 -2 +2	14 -2 +2	21 -2 +2	28 -2 [contact] -0 +2	57	63 -2 +2	70 -2 +2	77 -2 +2	84 -2 +0	91 -3 +3	
Informed consent	X															
Inclusion / Exclusion criteria	X	X							X ¹²							
Metabolite Screening Assay	X															
Corporate Confidential Information	X															
Randomization			X ¹⁰													
Contact IRT	X	X	X	X	X	X	X			X	X	X	X	X		
Study drug dispensation and administration in clinic in the morning			X	X	X	X	X			X	X	X	X	X		
Medical history/current medical conditions	X	X							X							
Concomitant therapies									X							
Demography	X															
Vital Signs	X	X	X ⁴	X ⁴	X ⁴	X ⁴	X ⁴		X	X ⁴	X ⁴	X ⁴	X ⁴	X ⁴	X	
Body height	X															
Body weight	X	X			X ⁴		X ⁴		X			X ⁴		X ⁴	X	
Physical examination	X	X			X ⁴		X ⁴		X			X ⁴		X ⁴	X	

EPOCH	SCREENING		TREATMENT PERIOD 1								TREATMENT PERIOD 2					
	Visit Name	Screening	Baseline	Day 1	Day 7	Day 14	Day 21	Day 28	Washout	Baseline/ET/EOS ²	Day 57	Day 63	Day 70	Day 77	Day 84	ET/EOS
Visit Numbers ¹	1	2	101	103	104	105	106		199	201	202	203	204	205	299	
Study Day(s)	-45 to -14	-7 to -4	1	7 -2 +2	14 -2 +2	21 -2 +2	28 -2 [contact] -0 +2	57	63 -2 +2	70 -2 +2	77 -2 +2	84 -2 +0	91 -3 +3	
Spirometry	X	X		X ⁴	X ⁴	X ⁴	X ⁴		X		X ⁴	X ⁴	X ⁴	X ⁴	X	
ECG evaluation	X	X			X ⁴		X ⁴		X			X ⁴		X ⁴	X	
Corporate Confidential Information			X			X		X				X			X	X
			X	X ⁴	X ⁴	X ⁴	X ⁴		X	X ⁴	X ⁴	X ⁴	X ⁴	X ⁴	X	
			X	X ⁴	X ⁴	X ⁴	X ⁴		X ¹³	X ⁹	X ⁹	X ⁹	X ⁹	X ⁹	X	
PK blood collection			X ⁹	X ⁹	X ⁹	X ⁹	X ⁹									
Central Lab Blood Chemistry ⁶	X	X	X ⁴	X ⁴	X ⁴	X ⁴	X ⁴		X	X ⁴	X ⁴	X ⁴	X ⁴	X ⁴	X	
Central Lab Hematology	X	X			X ⁴		X ⁴		X			X ⁴		X ⁴	X	
Hepatitis screen	X															
Corporate Confidential			X													
			X													
Alcohol Test, Drug Screen, and Cotinine Test	X	X								X						X
HIV screen	X															
Pregnancy test	X ⁷	X ⁸			X ^{4,8}		X ^{4,8}		X ⁸			X ^{4,8}		X ^{4,8}	X ⁸	
Urinalysis	X	X	X ⁴	X ⁴	X ⁴	X ⁴	X ⁴		X	X ⁴	X ⁴	X ⁴	X ⁴	X ⁴	X	
Telephone follow-up								X ³								
AEs and SAEs								X								

EPOCH	SCREENING		TREATMENT PERIOD 1								TREATMENT PERIOD 2					

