	Visit Name	Screening	Baseline	Day 1	Day 7	Day 14	Day 21	Day 28	Washout	Baseline/ET/EOS ²	Day 57	Day 63	Day 70	Day 77	Day 84	ET/EOS
Visit Numbers ¹	1	2	101	103	104	105	106		199	201	202	203	204	205	299	
Study Day(s)	-45 to -14	-7 to -4	1	7 -2 +2	14 -2 +2	21 -2 +2	28 -2 [contact] -0 +2	57	63 -2 +2	70 -2 +2	77 -2 +2	84 -2 +0	91 -3 +3	
Study Drug Questionnaire									X ¹³							X
Phase / Study completion information		X ¹¹							X ¹³							X

¹ Visit structure given for internal programming purpose only

² Baseline: For patients continuing onto study treatment period 2.

ET/EOS: Early Termination/End of Study: For subjects who undergo study/treatment discontinuation and subjects who withdraw prematurely

³ Telephone Contact on Day 42 (-5/+5) of Washout

⁴ Pre-dose

Corporate Confidential Information

⁶ Central lab collection: Sodium, potassium, bicarbonate, creatinine, BUN, uric acid, chloride, albumin, calcium, alkaline phosphatase, total bilirubin, LDH, GGT, AST, ALT, PT/INR, amylase, lipase, CK, glucose, total cholesterol, and triglycerides

⁷ Serum pregnancy test

⁸ Urine pregnancy test. If positive, drug must be withheld and a confirmatory serum pregnancy test must be sent

⁹ PK blood sample to be collected at 15 minutes after the start of inhalation of the morning dose

¹⁰ Randomization can occur any time between visits 2 and 101 after eligibility is confirmed

¹¹ Screening phase completion

¹² To be completed only for Baseline visit

¹³ To be completed only for ET/EOS (Early Termination/End of Study) visit

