11.6 Sample size calculation

Cohort 1 and 2: The first and second cohort will include 8 patients each, randomized 3:1 to drug: placebo. The sample size of 8 patients per cohort was based on practical considerations and clinical judgment that the numbers of patients are appropriate for the assessment of overall safety and tolerability and for providing adequate confidence for dose escalation. In cohort 1, for instance, an adverse event with an incidence of 23.5% will have a probability of 80% of occurring in at least one patient and a probability of 43% of occurring in two or more patients.

Cohort 3: Based on drop-out rate during the study, up to 40 patients may be randomized to cohort 3 to ensure that at least 24 complete both periods.

^C
Corporate Confidential Information

C

o

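### Cohort 3 is promised post-dose safety evaluations, but all 10 legible vital-sign readings at its dosing visits are pre-dose

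*Protocol*

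**What the plan says.** Protocol section 3.1 uses one sentence twice, first for Cohorts 1 and 2 and again for Cohort 3: "Post-dose evaluations will include routine safety evaluations and blood for PK assessments". Section 8.4 leaves the timing of each safety assessment to the assessment schedule, so Table 8-1 decides what sites do.

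In the Cohort 3 part of Table 8-1, the row "Study drug dispensation and administration in clinic in the morning" marks ten visits: Days 1, 7, 14, 21 and 28, and Days 57, 63, 70, 77 and 84. The vital-signs row has an entry at each of them, and each entry carries footnote 4, which means pre-dose. Footnote 9 gives the one legible timed item after the dose: "PK blood sample to be collected at 15 minutes after the start of inhalation of the morning dose".

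On dose, section 3.1 fixes the first step: "Cohort 1 will receive 3 mg bid dose (6 mg/day) or placebo over 1 week". Section 6.2 plans 6 mg bid for Cohort 2, but section 3.1 makes that cohort optional: "Cohort 2 may be skipped if safety, tolerability, PK and PD data from cohort 1 are found favorable to proceed directly to cohort 3". Section 3.3 sets the ceiling for Cohort 3: "The maximum dose in cohort 3 will be expected to not exceed 6 mg bid". Section 6.2 repeats that ceiling.

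SAP section 7.2 summarises Cohort 3 vital signs by day within period, with a single Day 1 time point.

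**The concern.** The text promises routine safety evaluations after dosing, and the schedule that governs conduct does not provide one in any legible row. A site that follows Table 8-1 would take vital signs, give the dose, draw PK blood at 15 minutes and have no further scheduled measurement. A symptom-free change in oxygen saturation, respiratory rate, pulse or blood pressure soon after the first inhalation would go unmeasured on QBW276 and on placebo alike.

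Section 6.9 itself anticipates that staff may want to evaluate a patient for bronchospasm after the study drug, and section 3.6 names close monitoring of vital signs among the measures that limit risk. Lighter monitoring in Cohort 3 is easier to defend if post-dose readings at the same dose already exist from Cohort 2. The protocol does not guarantee that they will.

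**Working it through.** The plan gives no figure for this point, so the check is a count of schedule entries, followed by the dose paths.

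**1. Vital-sign readings at dosing visits (Table 8-1 and the Cohort 1 and 2 detail tables)**

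| Cohort | Pre-dose | Post-dose | Post-dose share |
|---|---|---|---|
| 1 (legible) | Days 1, 2, 7 = 3 | Day 1 at 1 h and 6 h; Day 7 at 1 h = 3 | 3 of 6 |
| 2 | Days 1, 2, 7, 14 = 4 | Days 1 and 14, each at 1 h and 6 h = 4 | 4 of 8 |
| 3 (legible) | All ten dosing visits = 10 | none | 0 of 10 |

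The four Cohort 3 vital-sign entries without a footnote are at screening, baseline, visit 199 and visit 299, where no dose is given. For Cohort 1, a 6 h row on Day 7 is not visible in the available text, so 3 is a minimum.

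**2. Other Cohort 3 safety rows.** At dosing visits, the legible entries for ECG, chemistry, hematology, urinalysis, physical examination and spirometry are also pre-dose. On the two first-dose days (Days 1 and 57), the ECG and spirometry rows are blank.

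**3. Length of stay.** Section 3.1 keeps Cohort 1 and 2 patients in the clinic for at least 6 hours after the first dose. No such stay is legible for Cohort 3.

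**4. Dose paths before Cohort 3 starts.** Each of Cohorts 1 and 2 has 6 active patients.
- Cohort 2 run at 6 mg bid: 6 × 4 = 24 scheduled post-dose readings on 6 mg bid.
- Cohort 2 skipped: 0 above 3 mg bid. Cohort 1 supplies at least 6 × 3 = 18 on 3 mg bid.
- Cohort 3 dosed at 3 mg bid: covered by Cohort 1 on either path.

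Zero readings at the Cohort 3 dose therefore needs two things together: Cohort 2 is skipped, and Cohort 3 goes above 3 mg bid.

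**5. With one post-dose set on the first-dose day of each period.** Each completer has 2 readings, one on each treatment. For 24 completers that is 24 × 2 = 48, of which 24 are on QBW276 and 24 on placebo. If all 40 permitted patients were randomized and completed, it would be 40 × 2 = 80.

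**The case against.** **The sentence may mean evaluations after dosing has begun.** In the Cohort 3 paragraph it follows the statement on dosing for up to 28 days, it does not name vital signs, and the Day 7 to 28 visits are scheduled. This reading is strained. The next sentence introduces those visits separately, and the identical sentence for Cohorts 1 and 2 is put into effect with readings timed after the dose.

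**Post-dose safety is not absent.** This stands. A reader might infer that Cohort 3 has no post-dose safety monitoring, and the documents do not say so. AEs are sought at each visit (section 9.1), and sites may do unscheduled spirometry (sections 6.9 and 8.4.6). But the AE questioning is not tied to a time after the dose, and the spirometry is discretionary, guided in section 6.9 by signs and symptoms. Neither schedules a reading after the first inhalation.

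**The Cohort 2 skip is only a branch.** This also stands. Six mg bid is a ceiling, and the Cohort 3 dose needs sponsor and investigator review, DMC endorsement and a PK exposure-margin check. Those controls act before dosing and do not measure the acute response. The dose rationale is partly redacted, so post-dose readings at 6 mg or more may exist in healthy volunteers; the statement here is limited to this study's CF patients.

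**Bronchodilators blur the comparison.** Section 6.9 lets patients use one immediately before study drug, once lung function has been measured. A shift between the two readings could then partly reflect the bronchodilator. Use is voluntary and need not match between periods, so it has to be recorded.

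**Conclusion.** The mismatch is real and modest. In the legible schedule, 0 of 10 Cohort 3 vital-sign readings at dosing visits are post-dose, while the same sentence produces 4 of 8 in Cohort 2. It exists whether or not Cohort 2 runs, and is more serious on the path where Cohort 2 is skipped and Cohort 3 exceeds 3 mg bid.

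Two further inferences are tempting and not supported.
- Section 11.6 says of Cohort 1 that "an adverse event with an incidence of 23.5% will have a probability of 80% of occurring in at least one patient". This reproduces with 6 active patients (1 − 0.765^6 = 0.80), and the matching incidence for 24 patients is 1 − 0.2^(1/24) = 6.5%. A reader might credit the extra reading with that gain. The difference is only cohort size, and for AEs it already holds without the change.
- A reader might think it enough to reword section 3.1 and state that Cohort 3 relies on Cohort 2. No legible text says so, and it would conflict with the option to skip Cohort 2.

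The conclusion assumes that no redacted Cohort 3 row holds a post-dose safety reading. At least one redacted row has marks without a legible timing. The Period 2 PK marks sit one row above their label in the extracted table and are read here as PK draws.

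**What to change.** In Table 8-1, Cohort 3, add one post-dose vital-signs set on Days 1 and 57, the first-dose day of each period, taken around the existing 15-minute PK draw and without delaying it. Pulse oximetry and respiratory rate are already in the section 8.4.2 definition and should be included. Record any bronchodilator taken between the pre-dose and post-dose readings, with its time.

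In SAP section 7.2, summarise Day 1 pre-dose and post-dose vital signs separately, by treatment. SAP section 7.1 lists only blood pressure, pulse rate and body temperature as vital signs, so respiratory rate needs adding. Pulse oximetry is summarised under SAP section 6.2.5 and needs the same split.

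Cost: a few minutes of site time at two visits where the patient already waits for the draw, with no extra visit, blood sample or device. Staff must fit the set around a timed draw that uses specially handled tubes (section 8.5). The reading is not time-matched to the 1 h and 6 h readings of Cohorts 1 and 2; a 1 h set would match better but would lengthen the visit. It does not measure bronchospasm directly and says nothing about later electrolyte changes. Sample size and the primary analysis are unaffected.

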3.2 Rationale for study design

Corporate Confidential Information

Cohort 3 is designed as a cross-over study which is a more powerful design requiring fewer patients than a parallel group design. Parallel group designs have significant between patient variability in percent of predicted FEV₁ (primary outcome); hence, a cross-over design will allow for each patient to be his/her own control.

The use of a placebo arm in both parts of the study is to provide a comparison group for an unbiased collection of safety, tolerability, PK/ , and efficacy data in a blinded manner.

The rationale to allow CFTR modulators (correctors, potentiators, etc), chronic inhaled and systemic antibiotics Corporate Confidential Information during the study is related to the fact that many patients are/will be treated with these drugs as routine standard of care. Some CF patient's standard of care regimen may include treatment with systemic antibiotics on a chronic basis. Some CF patients with chronic respiratory infections are prescribed inhaled antibiotics (for instance Tobramycin or vancomycin) which are alternately cycled after 4 weeks of therapy, or patients may have a 4 week antibiotic holiday between two 4 week antibiotic cycles.

Corporate Confidential Information

3.3 Rationale of dose/regimen, duration of treatment

Cohorts 1 and 2: Up to 16 patients with CF (8 patients in each cohort, regardless of genotype) will complete 7 to 14 days of inhaled QBW276 or placebo via the concept 1 inhaler. Cohort 1 will receive 3 mg bid dose, which is based on safety, tolerability, PK and adverse event data obtained from the CQBW276X2101 healthy volunteer study.

Cohort 3: Cohort 3 will be restricted to CF patients who are homozygous for the F508del mutation, Corporate Confidential Information

This may also help reduce variability in baseline characteristics of patients in this small study. Patients will receive 4 weeks of drug and 4 weeks of placebo, separated by a washout period of approximately 3 to 4 weeks in patients who cycle inhaled antibiotics. Washout period may be shortened to 2 weeks in patients who do not cycle inhaled antibiotics. For patients on cyclic inhaled antibiotics, the baseline visit will be on approximately the 7th day (0/+3 days) of inhaled antibiotic use during their 28 day antibiotic cycle. Patients who use the same inhaled antibiotic throughout the year may start the study on any antibiotic day. Patients will take their inhaled antibiotic therapy at approximately the same time during the study as they would usually at home Corporate Confidential Information

Cohort 1 - The first cohort will be dosed at 3 mg bid to begin assessment of safety and tolerability in CF because this dose has been
and found to be safe and well tolerated. Corporate Confidential Information
Corporate Confidential Information

The dose and frequency will be proposed by the sponsor at the data review, and will require approval from the designated site Investigator(s) and endorsement from the independent DMC. The maximum dose in cohort 3 will be expected to not exceed 6 mg bid. Corporate Confidential Information

PK data will be assessed after each dose cohort completes the study to confirm that an appropriate exposure margin exists before escalating to the next dose level.

Corporate Confidential Information

Cohort 3 –The dose selected for cohort 3 will be one that is expected to be safe and well-tolerated over 4 weeks of treatment based on blinded data obtained from cohorts 1 and 2 after 7 to 14 days of treatment. If a maximum tolerated dose for patients with CF (MTD) is identified in cohorts 1 or 2 on the basis of dose-limiting toxicity, the predicted exposure at the maximum planned dose in cohort 3 shall not exceed the exposure at the MTD. If an MTD is not defined

in cohorts 1 or 2, the maximum planned dose in cohort 3 shall not exceed the systemic exposure cap based on pre-clinical data. The efficacy of the proposed dose will be justified by the lung function measurements which will be conducted during cohorts 1 and 2. Corporate Confidential Information

